#### **9.1.4.3 *Fasting plasma glucose measurement***

Plasma glucose is measured in the fasting state at Screening (Visit 1) and all on-site visits during the treatment period. For the eligibility and efficacy assessments of the study, FPG is measured at a central laboratory to allow estimation of change from Baseline to Week 26 in FPG.

#### **9.1.4.4 *Body weight measurement***

Body weight is measured at all on-site visits to allow the estimation of change from Baseline to Week 26 in body weight and reduction in body weight by  $\geq 2\%$ ,  $\geq 5\%$ , and  $\geq 10\%$  from Baseline.

Body weight should be obtained with the patient wearing undergarments or very light clothing and no shoes, and with an empty bladder. The same scale should be used throughout the study, and calibrated on a regular basis as recommended by the manufacturer.

The same scale should be used throughout the study, and calibrated on a regular basis as recommended by the manufacturer. Calibration should be documented in source documents. The use of balance scales is recommended. The floor surface on which the scale rests must be hard and should not be carpeted or covered with other soft material. The scale should be balanced with both weights at zero and the balance bar aligned. The patient should stand in the center of the platform as standing off-center may affect measurement. The weights are moved until the beam balances (the arrows are aligned). The weight is read and recorded in the e-CRF and Source Data. Self-reported weights are not acceptable; patients must not read the scales themselves.

#### **9.1.4.5 *Blood pressure measurements***

Systolic BP and DBP will be assessed at all on-site visits. Blood pressure measurements must be taken as described in [Section 9.2.1.4](#) with details provided in [Appendix D](#).

#### **9.1.4.6 *Kidney function parameter measurement***

Urine albumin, creatinine and glucose, and serum creatinine are assessed at Baseline (Visit 3) and all subsequent on-site visits. A central laboratory will analyze samples and estimate change from Baseline in urine ACR, UGE, urine GCR, serum creatinine and eGFR (by the 4 variable MDRD equation). To prevent partial unblinding, UGE and GCR results will be masked to investigational sites.

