#### 9.2.1.3.1 Urinalysis

Urinalysis (urine dipstick with microscopy) by central laboratory will be performed at Screening (Visit 1), Baseline (Visit 3) and Week 26 (Visit 9). To prevent partial unblinding, UGE results will be blinded to investigational sites and patients, and the central laboratory urine dipstick will not include the measurement of urine glucose. Central urinalysis includes:

- Urine dipstick includes: specific gravity, pH, protein, blood, ketones, bilirubin, urobilinogen, nitrite, and leukocyte esterase
- Urine microscopy includes, but is not limited to: detection of formed cellular elements, casts, bacteria, yeast, parasites, and crystals in centrifuged urine sediment

In the event of abnormal urinalysis findings suspicious of urinary tract infection, urine culture should be performed. Positive urine culture determination will be based upon the criteria of the reporting laboratory.

If the urine dipstick is positive for blood, the central laboratory will perform reflexive testing to include microscopy. Additional testing will be performed according to the judgment of the Investigator. Referral to urology/urologic evaluation is recommended for new or unexplained cases of confirmed hematuria (urology/urologic evaluation is not required where hematuria is considered to be related to diabetic nephropathy).

In addition, urine albumin, calcium, glucose and creatinine will be assessed at Baseline (Visit 3) and all subsequent on-site visits.

Urine markers of bone and calcium metabolism will be assessed at Baseline (Visit 3), and Week 26 (Visit 9), and include: calcium and phosphorus. Serum markers of bone and calcium metabolism are listed in [Table 2](#).

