Endpoints for evaluating renal function include eGFR, based on serum creatinine, and urine albumin to creatinine ratio as well as routine monitoring of urine via dipstick and microscopy. UGE and urine GCR are other valid markers of renal function, and will be assessed at appropriate time points in this study.

Due to potential effects on bone and calcium metabolism, specific biomarkers for bone and calcium metabolism will be assessed at regular time points. In view of the SGLT1 inhibitory effects in the GI tract, specific markers of intestinal transit and absorption will also be measured.

The other efficacy and safety assessments in this study are standard, well-established measurements for a Phase 3 study evaluating the treatment of T2D in adult participants.

The length of the study is considered appropriate for detection of the primary endpoint given the power estimates (see [Section 11](#)).

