### **Maintaining Hydration:**

Sodium-glucose cotransporter type 2 inhibitors are associated with osmotic diuresis and volume depletion, which may lead to dizziness or hypotension, especially in the elderly. Before initiating study drug (at Screening, Run-in and Randomization) and during all on-site study visits thereafter, assess volume status in patients with renal impairment, the elderly, in patients with low SBP, or if receiving diuretics, angiotensin-converting-enzyme inhibitors, or angiotensin receptor blockers. All patients will be advised to maintain proper fluid intake and to consider increasing it if they sense greater thirst, more urine production, or if they feel dizzy or faint.

Patient communication cards will be printed with the following for patients with T2D:

“The following advice may be useful in helping you to maintain proper hydration and prevent dehydration:

- Dehydration is when your body loses too much fluid, frequently due to diarrhea or increased urination

- Consider increasing the amount of fluids you drink if:
  - You sense greater thirst than usual
  - You have a dry mouth or cracked lips
  - You have a fever
  - You have diarrhea or vomiting
  - You urinate more frequently or in larger amounts than usual
  - You get up in the middle of the night to urinate (more than usual)
  - You feel dizzy or light-headed
  - You exercise, or when it is hot outside”

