- Urine microscopy includes, but is not limited to: detection of formed cellular elements, casts, bacteria, yeast, parasites, and crystals in centrifuged urine sediment
- Urine markers of bone and calcium metabolism: calcium and phosphorus.
- Urine albumin, calcium, glucose and creatinine

Serum glucose, UGE, calculated urine ACR and calculated urine GCR will be presented as efficacy parameters in [Section 2.4.4](#). For creatinine and calculated eGFR, PCSA summaries will be presented in the safety section while descriptive summaries in the efficacy section.

Technical formulas are described in [Section 2.5.1](#).

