2.5 DATA HANDLING CONVENTIONS

2.5.1 General conventions

The following formulas will be used for computation of parameters.

HbA1c

The formula to convert HbA1c from Diabetes Control and Complications Trial (DCCT) aligned value to International Federation of Clinical Chemistry and Laboratory Medicine (IFCC) standardized value is,

Statistical Analysis Plan

Version: 3

Lexicon Pharmaceuticals Protocol No. EFC14833

Date of Issue: 21-Nov-2019

Covance Study ID: 000000150524

IFCC-HbA1c (mmol/mol) = [DCCT-HbA1c (%) - 2.15] x 10.929.

Renal function formulas

The estimated GFR (mL/min/1.73 m²) will be calculated using the 4 variable Modification of Diet in Renal Disease (MDRD) formula:

Standard unit: eGFR (mL/min/1.73 m²) = 175 x [Serum Creatinine (μmol/L)/88.4]^{-1.154} x Age (year)^{-0.203} x 1.212 (if Black) x 0.742 (if female)

Conventional unit: eGFR (mL/min/1.73 m²) = 175 x Serum Creatinine (mg/dL)^{-1.154} x Age (year)^{-0.203} x 1.212 (if Black) x 0.742 (if Female)

Urine ACR

Standard unit: Urine ACR (mg/g) = Urine Albumin (mg/dL) / [Urine Creatinine (mmol/L) x 11.31] x 1000

Conventional unit: Urine ACR (mg/g) = Urine Albumin (mg/dL) / Urine Creatinine (mg/dL) x 1000

Urine GCR

Standard unit: Urine GCR = Urine Glucose (mmol/L) / Urine Creatinine (mmol/L)

Conventional unit: Urine GCR = Urine Glucose (mg/dL) / Urine Creatinine (mg/dL)

Calculation of LDL-C

When TG is lower than or equal to 4.52 mmol/L (400 mg/dL), LDL-C is calculated using the Friedewald equation as:

- in standard unit (mmol/L), TC – HDL-C – TG/2.17;
- in conventional unit (mg/dL), TC – HDL-C – TG/5.

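### Urinary calcium and phosphorus are planned as raw values from visit urine samples; because the drug class is linked to diuresis, creatinine ratios should be their main summary

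*Protocol*

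**What the plan says.** **Calcium and phosphorus.** Protocol 9.2.1.3.1 states: "Urine markers of bone and calcium metabolism will be assessed at Baseline (Visit 3), and Week 26 (Visit 9), and include: calcium and phosphorus". The same section adds that "urine albumin, calcium, glucose and creatinine will be assessed at Baseline (Visit 3) and all subsequent on-site visits". SAP 2.1.4.4 repeats the markers without a denominator: "Urine markers of bone and calcium metabolism: calcium and phosphorus". SAP 2.4.5.4 then summarises the laboratory's reported values and their changes from baseline by visit and treatment group. Parameters without a PCSA criterion are also tabulated against the normal range. SAP Appendix B has no criterion for urinary calcium or phosphorus.

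**Glucose.** Protocol 9.1.4.6 says "Urine albumin, creatinine and glucose, and serum creatinine are assessed at Baseline (Visit 3) and all subsequent on-site visits", and then: "A central laboratory will analyze samples and estimate change from Baseline in urine ACR, UGE, urine GCR, serum creatinine and eGFR". SAP 2.5.1 gives formulas for the albumin-creatinine ratio (ACR) and GCR, each with urine creatinine from the sample as denominator. It gives no formula for UGE.

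**Collection.** The flow charts and the visit lists in Protocol 10.1 schedule urine analytes by visit. None mentions a timed collection or a measured volume.

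**Diuresis.** Protocol Appendix C states: "Sodium-glucose cotransporter type 2 inhibitors are associated with osmotic diuresis and volume depletion". It gives no size.

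**The concern.** A urine concentration is an amount excreted divided by a volume. If the drug raises the volume, the concentration falls even when the amount is unchanged. Randomisation does not remove this, because the volume change would itself be an effect of treatment and so would differ by arm.

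Protocol 9.6 says the bone and calcium markers are measured because of potential effects on bone and calcium metabolism, and fractures are adjudicated events. For the urinary markers, a modest rise in calcium or phosphorus excretion on sotagliflozin is a result one would want to see, and raw concentrations are the form in which dilution could hide it. The normal-range tables have the same weakness, since dilution alone could move a patient across a limit. The SAP plans no later model that would correct the descriptive tables.

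**Working it through.** The documents state no figure for urinary calcium, phosphorus or UGE, so there is none to reproduce.

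**Inputs**
- From the documents: urine calcium and creatinine are measured at Visit 3 and every later on-site visit, and urine phosphorus at Visit 3 and Visit 9 (Protocol 9.2.1.3.1). Creatinine is therefore available at both visits where the bone markers are taken. Diuresis is stated for the class without a size (Appendix C).
- Assumed: V, the fractional rise in urine volume on sotagliflozin relative to placebo, from 5 to 50%, with 10 to 30% as the central range.
- Assumed for illustration: E, the true ratio of excretion to baseline.

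**Formulas**
- Ratio of raw concentration to baseline = E / (1 + V).
- Ratio of analyte/creatinine to baseline = [E / (1 + V)] / [1 / (1 + V)] = E, if creatinine excretion is unchanged.

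**Raw concentration, apparent change from baseline**

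| V | E = 1.0 | E = 1.1 | E = 1.2 | E = 1.3 |
|---|---|---|---|---|
| 5% | −4.8% | +4.8% | +14.3% | +23.8% |
| 10% | −9.1% | 0.0% | +9.1% | +18.2% |
| 20% | −16.7% | −8.3% | 0.0% | +8.3% |
| 30% | −23.1% | −15.4% | −7.7% | 0.0% |
| 50% | −33.3% | −26.7% | −20.0% | −13.3% |

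For example, 1/1.10 − 1 = −9.1%, and 1/1.30 − 1 = −23.1%. A true rise in excretion equal to V reads as no change; a smaller one reads as a fall. A true 20% rise reads as +9.1% at V = 10%, as nothing at V = 20%, and as −7.7% at V = 30%.

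**With the creatinine ratio**, V cancels: unchanged excretion reads 0% and a true 20% rise reads +20% at every V above. If creatinine excretion itself changed by a factor C, the ratio would read E/C. That error does not depend on urine volume.

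**Glucose.** With an assumed fivefold rise in excretion (E = 5), the bare concentration reads 5/1.05 − 1 = +376% at V = 5% and 5/1.50 − 1 = +233% at V = 50%. GCR reads the full +400%. Dilution understates a large rise but does not conceal it.

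**The case against.** **The dilution is not shown.** Appendix C makes a class statement without a size, and no passage gives the effect of sotagliflozin on the concentration of a visit sample. Patients attend Visits 1 to 9 fasting (Protocol 10.1), and hydration advice goes to all patients, so placebo urine may also be diluted at times. This stands: the size is assumed, and the downward bias is plausible rather than demonstrated.

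**Other markers address the same question.** Serum calcium, phosphorus, PTH, both vitamin D forms, NTX, β-CTX-1 and P1NP are also measured, and fractures are adjudicated blind. None of these depends on urine dilution. This stands too, and it limits the consequence to the two urinary markers.

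**Nothing is lost.** The ratios can be derived at any time from data already collected, and safety laboratory data carry no systematic testing. That is correct, and it is why the severity is low. It does not make the raw concentration a good main summary.

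**A laboratory manual may specify the collection.** It may, but the protocol cites a manual only for handling PK samples (9.3.1.2), and the SAP would still lack the ratios and a UGE formula.

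**Stronger readings to avoid.** A reader might infer that the design cannot show a change in urinary glucose. The documents do not support this: GCR is a planned endpoint beside UGE and is divided by creatinine.

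A reader might also infer from Protocol 9.6, which says "UGE and urine GCR are other valid markers of renal function", that a drug-driven rise in GCR would be reported as a renal finding. That wording is loose, but Protocol 4.4 attributes higher UGE to SGLT2 inhibition, the results are masked because they could unblind, and the renal events in SAP Table 3 rest on eGFR, dialysis, transplant and renal death.

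**Conclusion.** The point holds for urinary calcium and phosphorus. As planned, a change in either marker cannot be read as a change in excretion, because no volume is described, no creatinine correction is specified, and the protocol itself links the class to diuresis. On an assumed volume rise of 10 to 30%, unchanged excretion would read as a 9 to 23% fall, and a true rise of the same 10 to 30% could read as no change. The documents do not establish that this will happen, only that the planned summary cannot exclude it.

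For glucose, what remains is a matter of definition. UGE is named as an objective and an endpoint but has no formula, and an amount excreted cannot be derived from the sampling described.

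Severity is low. UGE and GCR are among the other endpoints, which are descriptive; calcium and phosphorus are descriptive safety markers; none is in the testing hierarchy.

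**What to change.** - In SAP 2.5.1, add formulas for urine calcium/creatinine and urine phosphorus/creatinine, using creatinine from the same visit as is already done for GCR.
- In SAP 2.1.4.4, make these ratios the main summary of the urinary bone and calcium markers, and keep the raw concentrations as supportive.
- In the SAP's endpoint and laboratory sections, label the raw glucose value as urine glucose concentration, and state that conclusions about urinary glucose rest on GCR. The stated UGE objective need not be removed; the SAP should say that no amount excreted is derived.

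The cost is two derived variables, their tables and some wording, with no new samples or visits. The downside is that the ratio assumes creatinine excretion is unchanged by treatment. The SAP should state that assumption, and keeping the raw values lets a reader see both.

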#### **9.1.4.7 *Proportion of patients requiring rescue for hyperglycemia***

The use of rescue medications for hyperglycemia will be assessed and reported throughout the treatment period. Routine alerts on FPG will be sent to the Investigator from the central laboratory to ensure that glycemic parameter results remain within predefined thresholds. For details and further actions should FPG values fall above thresholds, refer to [Section 8.2.1](#).

## **9.2 SAFETY ENDPOINTS**

Assessments for safety include AEs, SMBG, clinical laboratory assessments, physical examination, electrocardiogram (ECG), weight, and vital signs. An independent DMC will meet on a regular basis to review accumulating clinical trial safety data.

Adjudication of all deaths, MACE/other selected CV events (MI, stroke, unstable angina leading to hospitalization, and heart failure leading to hospitalization), selected renal events, bone fracture, and DKA will be performed in a blinded manner by a CEC(s) comprised of experts. Details will be provided in the charter of the CEC(s). Further details are available in [Section 6.4.2](#).

Two expert committees will review all potential cases of DILIs and cases of amputation in a treatment-blinded manner to evaluate causality.

The following safety endpoints will be assessed:

- Adverse events, AEs leading to discontinuation from the IMP, adverse events of special interest (AESIs), Events of Special Interest (EOSIs), SAEs and deaths
- Hypoglycemia (all, severe, and/or documented symptomatic hypoglycemia)
- Clinical laboratory results (including fasting lipids; see [Section 9.2.1.3](#)), vital signs and ECG results
- Markers of bone and calcium metabolism
- Markers of intestinal transit and absorption

## **Observation period of safety endpoints**

The observation period of safety data will be divided into 3 segments:

- The pre-treatment period is defined as the time between the date of the informed consent and the first dose of double-blind IMP.
- The on-treatment period (TEAE period) is defined as the time from the first dose of double-blind IMP up to 10 days (1 day for hypoglycemia) after the last dose of double-blind IMP, regardless of the introduction of rescue therapy. The 10-day interval is chosen based on the half-life of the IMP (approximately 5 times the half-life of sotagliflozin) in patients with moderate renal dysfunction.
- The post-treatment period is defined as the time starting 11 days after the last dose of double-blind IMP (after the on-treatment period).

The baseline value for safety endpoints in the safety population is the last available value (or the average of all values for creatinine or eGFR) prior to the first administration of the double-blind IMP.

### **9.2.1 Assessment methods of safety endpoints**

#### **9.2.1.1 Adverse events**

Adverse events including SAE, AESI and EOSI will be assessed. Refer to [Section 10.4](#) to [Section 10.6](#) for details.

##### *9.2.1.1.1 Adverse Events of Special Interest*

Adverse Events of Special Interest are listed in [Section 10.4.1.3](#), reporting requirements for AESI are presented in [Section 10.4.4](#).

##### *9.2.1.1.2 Events of Special Interest*

Events of Special Interest are separate from AESIs. For a list of events defined as EOSIs and their reporting requirements see [Section 10.4.1.4](#) and [Section 10.4.5](#), respectively.

#### **9.2.1.2 Hypoglycemia**

Hypoglycemia will be assessed from Visit 2 onwards and continue until 4 weeks after the last dose of IMP (note: for patients who discontinue treatment before Week 26, safety data will be collected until scheduled study end). Patients will also complete the hypoglycemia log (as part of the patient diary) from Visit 2 onwards, which will be regularly reviewed by Investigators. See [Section 10.6.1](#) for further details.

### 9.2.1.3 **Laboratory safety variables**

The clinical laboratory data consist of blood analysis (including hematology, clinical chemistry, amylase, lipase, lipid profile) and urinalysis, according to the schedule presented in [Section 1.2](#). Clinical laboratory values will be analyzed after conversion into standard international units. International units will be used in all listings and tables. [Table 2](#) lists the hematology, clinical chemistry and other blood safety parameters to be assessed by the central laboratory.

Alerts to the Investigator are set up for specific laboratory abnormalities. Investigators should review these alerts and follow-up if needed as per his/her medical judgement. Re-tests at central laboratory are acceptable if needed.

In addition, for WOCBP a serum pregnancy test is performed at Screening and urine pregnancy tests are taken at all on-site visits during the double-blind Treatment Period excluding Visit 4 (Week 1). Any positive urine test results must be confirmed by a serum pregnancy test. The Investigator may perform additional tests at their discretion or as required by local regulations.

For women of nonreproductive potential ([Appendix A](#)), follicle-stimulating hormone (FSH) and/or estradiol levels should be tested if the definition of postmenopausal or premenopausal cannot be satisfied, eg, no medical document of hysterectomy or cessation of menses <12 months without an alternative medical cause.

**Table 2 – Serum chemistry parameters**

Clinical chemistry	Hematology	Other blood parameters
Sodium	Complete blood count (CBC)	Lipid profile
Potassium	Differential	Total cholesterol (TC)
Chloride	Platelet count	High-density lipoprotein cholesterol (HDL-C)
Carbon dioxide (bicarbonate)	Hemoglobin	Low-density lipoprotein cholesterol (LDL-C) will be calculated by Friedwald equation
Blood urea nitrogen (BUN)	Hematocrit	Non-HDLC will be calculated as the difference between TC and HDLC
Creatinine (eGFR will be calculated)		Triglycerides (TG)
Glucose (serum)		Blood Markers of Intestinal Transit and Absorptiona
Alanine aminotransferase (ALT)		Vitamins: B6, B12, K, E, A
Aspartate aminotransferase (AST)		Serum folate
Total bilirubin (TB)		Ferritin
Alkaline phosphatase (ALP)		Markers of bone and calcium metabolismb
Uric acid		Calcium
Calcium		25-hydroxyvitamin D
Phosphorus		1,25-dihydroxyvitamin D
Total protein		Phosphorus

Clinical chemistry	Hematology	Other blood parameters
Albumin		Parathyroid hormone (PTH)
Magnesium		Markers of bone resorption: N-terminal telopeptide (NTX), beta-C-terminal telopeptide ( $\beta$ -CTX-1)
Creatine phosphokinase (CPK)		Marker of bone formation: type 1 procollagen N-terminal (P1NP)
Lactic acid dehydrogenase (LDH)		
Amylase		
Lipase		

All assessments to be performed by central laboratory.

All assessment measured in serum.

a To be collected at Baseline (Visit 3), Week 26 (Visit 9), and Follow-up Visit (Visit 10).

b To be collected at Baseline (Visit 3) and Week 26 (Visit 9). Urine markers of bone and calcium metabolism are listed in [Section 9.2.1.3.1](#).

#### 9.2.1.3.1 Urinalysis

Urinalysis (urine dipstick with microscopy) by central laboratory will be performed at Screening (Visit 1), Baseline (Visit 3) and Week 26 (Visit 9). To prevent partial unblinding, UGE results will be blinded to investigational sites and patients, and the central laboratory urine dipstick will not include the measurement of urine glucose. Central urinalysis includes:

- Urine dipstick includes: specific gravity, pH, protein, blood, ketones, bilirubin, urobilinogen, nitrite, and leukocyte esterase
- Urine microscopy includes, but is not limited to: detection of formed cellular elements, casts, bacteria, yeast, parasites, and crystals in centrifuged urine sediment

In the event of abnormal urinalysis findings suspicious of urinary tract infection, urine culture should be performed. Positive urine culture determination will be based upon the criteria of the reporting laboratory.

If the urine dipstick is positive for blood, the central laboratory will perform reflexive testing to include microscopy. Additional testing will be performed according to the judgment of the Investigator. Referral to urology/urologic evaluation is recommended for new or unexplained cases of confirmed hematuria (urology/urologic evaluation is not required where hematuria is considered to be related to diabetic nephropathy).

In addition, urine albumin, calcium, glucose and creatinine will be assessed at Baseline (Visit 3) and all subsequent on-site visits.

Urine markers of bone and calcium metabolism will be assessed at Baseline (Visit 3), and Week 26 (Visit 9), and include: calcium and phosphorus. Serum markers of bone and calcium metabolism are listed in [Table 2](#).

